2.3. Definition of Subgroups

See [Table 3](#) for the definitions of all the subgroups. The third column in the table indicates for which endpoints the subgroup is applied.

Descriptive statistics will be produced for the different subgroups.

In demographics and baseline disease characteristics, the following subgroups will be used:

- Region
- Influenza A subtype category
- Treatment extension
- Age group
- Time since onset of influenza symptoms (actual: ≤ 72 hours, >72 hours)
- Time since onset of influenza symptoms (actual: ≤ 48 hours, $>48 - 72$ hours, >72 hours)
- Type of SOC at baseline (actual)
- NEWS2 at screening (actual)
- Baseline resistance
- Any baseline polymorphism
- Influenza season
- Study Period
- COVID-19 impacted

Stratification factors (actual) will be used as subgroups for concomitant medication.

For the primary and the six most important secondary endpoints (i.e.: All endpoints included in the hierarchy testing) the subgroup with subgroup*treatment interaction term will be added in the statistical analysis models, except for the study period subgroup, where the analysis will be performed separately for each individual category of the subgroup. For further details see [Section 5.2.3.](#) and [Section 5.3.2.](#) For other endpoints, the statistical analysis will be performed separately for each individual category of the subgroup.

Table 3: Subgroups with their definition

Subgroup	Definition	Endpoints
Region	Based on country according to UN classification of Geographic regions ^[9] : 
 • Europe/Africa • Northern-America • Latin America and the Caribbean • Asia and Oceania 	- Efficacy (primary and secondary endpoints, excluding viral kinetics endpoints)
Age group (years)	
 • 13-17 years • 18-65 years • 66-85 years 	- Efficacy (primary and secondary endpoints, excluding viral kinetics endpoints) - All Safety
NEWS2 at screening (actual)	
 • 4-5 • ≥ 6 	- All Efficacy - Viral Phenotype - Viral Genotype
Type of SOC at baseline (actual)	
 • SOC including influenza antiviral treatment • SOC not including influenza antiviral treatment 	- All Efficacy - Viral Phenotype - Viral Genotype - Safety(AE summary, AEs and SAEs by MedDRA system organ class and preferred term, , influenza-related complications, laboratory toxicity)
Time (hours) from onset of influenza symptoms to first study drug intake (actual)	
 • ≤ 72 hours • $>72 - 96$ hours 	- All Efficacy - Viral Phenotype - Viral Genotype - Safety(AE summary, AEs and SAEs by MedDRA system organ class and preferred term, , influenza-related complications, laboratory toxicity)
Time (hours) from onset of influenza symptoms to first study drug intake (actual) – 3 categories	
 • ≤ 48 hours • $>48 - 72$ hours • $>72 - 96$ hours 	- All Efficacy - Viral Phenotype - Viral Genotype
Influenza A subtype category	
 • A/H1N1 • A/H3N2 • Other 	- Primary endpoint - The six most important secondary endpoints - All viral kinetics - Viral phenotype - Viral genotype
Hospitalization status	
 • Hospitalized • Outpatient 	- Only CM TLFs
Treatment extension	
 • Extended treatment • No extended treatment 	- All Efficacy - Viral Phenotype - Viral Genotype

Subgroup	Definition	Endpoints
Baseline polymorphism (based on influenza PB2 genotype)	Polymorphism on one or any of these amino-acid positions of interest: 
 • Q306 • F323 • S324 • F325 • S337 • H357 • F363 • K376 • T378 • F404 • Q406 • M431 • N510 	
 - Primary endpoint - Viral Phenotype - Viral Genotype - Viral kinetics
Baseline Resistance (Based on influenza PB2 phenotype)	Based on fold change (FC) in EC ₅₀ for pimodivir: 
 • FC≤4 • FC>4 	
 - Primary endpoint - Viral Phenotype - Viral Genotype - Viral kinetics
Influenza Season	
 • Northern Hemisphere 2017/2018 • Southern Hemisphere 2018 • Northern Hemisphere 2018/2019 • Southern Hemisphere 2019 • Northern Hemisphere 2019/2020 • Southern Hemisphere 2020 and so on to capture all enrolled subjects	
 - Efficacy (primary and the six most important secondary endpoints only) - All viral kinetics - Viral phenotype - Viral genotype
Study period	
 • pre interim (subjects enrolled for the interim analysis, i.e.: randomized before or on February 28, 2020) • post interim (subjects enrolled after the interim analysis, i.e.: randomized after February 28, 2020) 	
 -Efficacy (primary and the six most important secondary endpoints only) -safety (Safety(AE summary, AEs and SAEs by MedDRA system organ class and preferred term, influenza-related complications, laboratory toxicity))
COVID-19 impacted	
 • Yes • No COVID-19 impacted is based on any COVID-19 related AEs, COVID-19 related PD, any COVID-19 related treatment or study withdrawal	
 -Efficacy (primary and the six most important secondary endpoints only) - Safety (AE summary, AEs and SAEs by MedDRA system organ class and preferred term, influenza-related complications, laboratory toxicity)

Subjects enrolled from 1st October 2017 to 31th March 2018 are considered to be in the Northern Hemisphere 2017/2018 category and subjects enrolled from 1st April 2018 to 30st September 2018 are considered to be in the Southern Hemisphere 2018 category. Subjects enrolled from 1st October 2018 to 31th March 2019 are considered to be in the Northern Hemisphere 2018/2019 category and subjects enrolled from 1st April 2019 to 30st September 2019 are considered to be in the Southern Hemisphere 2019 category, and so on.

Note: The six most important secondary endpoints are: incidence in post-baseline complications, time to hospital discharge, time from ICU admission to ICU discharge, time to return to daily activities, time from start of mechanical ventilation to end of mechanical ventilation, rate of re-hospitalization.

Additional subgroup analysis may be specified in a separate analysis plan and reported separately from the clinical study report.

2.4. Study Day and Relative Day

Reference date refers to the start date of the first study drug administration. All efficacy and safety assessments at all visits will be assigned a day relative to this date.

The relative day (*reldy*) will be defined as:

$$\begin{aligned} \text{reldy} &= \text{visit date} - \text{reference date} + 1 \text{ for visits on or after the reference date,} \\ \text{reldy} &= \text{visit date} - \text{reference date} \text{ for visits before the reference date.} \end{aligned}$$

Consequently there is no 'day 0' defined.

2.5. Baseline and Endpoint

The baseline analysis visit is defined as the last assessment before the first intake of the study drug, with the possible exception for height, weight, viral load results from the central lab testing and the hospital recovery scale (HRS). Height and weight are only recorded once, at screening/baseline visit, and the values recorded at this visit will be allocated to the baseline analysis visits irrespective of start of study drug. For viral load, if no measurement is available prior to first dose of study drug, then the first result from the central lab testing obtained up to and including 30 minutes after first dose of study drug will be considered as the baseline assessment and will be flagged in the analysis dataset. The baseline HRS is defined irrespective of the time of the start of study drug, and is covering the screening/baseline/day 1 visit which may be performed over two days as defined per protocol. Baseline HRS will be assigned to Day 1.

As specified in the protocol, an ECG recording within 1 calendar day before signing of the ICF/assent form can be used as baseline ECG requirement, if no ECG measurement was performed between signing ICF and first study drug intake.

For programming purposes the baseline record will be doubled in the ADAM datasets, the doubled record will be renamed with AVISIT = 'Baseline', AVISITN = 0 and will be assigned to the treatment phase.

For vital signs, NEWS2, ECG and central laboratory data the last study visit (Endpoint) is defined as the last scheduled study visit/timepoint and will be either the final study visit (day 28) or the safety follow-up visit.

For viral phenotyping, the last visit (Endpoint) is defined as the last study visit/timepoint for which an EC₅₀ and/or IC₅₀ result is available (including unscheduled visit results).

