1.4. Sample Size Justification

The study will enroll 600 subjects between the ages of 13 and 85 years, inclusive. Subjects will be randomized 1:1 to one of the treatment arms.

The sample size is based on the primary endpoint of the hospital recovery scale at Day 6. Based on the proportional odds model and assuming a benefit of approximately 38% reduction of the common odds ratio, a total sample size of 600 subjects (randomized 1:1) is required to obtain a power of 90% [11]. Inclusion of stratification factors would provide some improvement on the derived power.

In the sample size calculation it is assumed that the distribution of subjects treated with placebo in combination with SOC treatment will be as follows on Day 6:

- Not hospitalized: 30%
- Non-ICU hospitalization, not requiring supplemental oxygen: 30%
- Non-ICU hospitalization, requiring supplemental oxygen: 25%
- Admitted to the ICU, not requiring invasive mechanical ventilation: 5%
- Requiring invasive mechanical ventilation: 5%
- Death: 5%

This sample size is robust to mild to moderate changes in this distribution.

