5.1. Analysis Specifications

5.1.1. Level of Significance

The population used for the evaluation at the final analysis will depend on the outcome scenario of the interim analysis: i.e.; scenario 1: continue with the full study population or scenario 2: continue only with the subjects with an onset of symptoms less than 72 hours before first study drug intake. Tables/graphs/listings will account for the selected scenario.

As a confirmatory strategy, to account for multiplicity in the statistical evaluation of the most important efficacy endpoints, in either scenario, a combination of hierarchical testing and the Bonferroni-Holm testing procedure will be applied to control for the overall Type I error rate at the 5% level. The following endpoints are included in the confirmatory strategy:

1. Hospital recovery scale at Day 6, ie, primary endpoint
2. Incidence in post-baseline complications
3. Time to hospital discharge
4. Time from ICU admission to ICU discharge
5. Time to return to daily activities
6. Time from start of mechanical ventilation to end of mechanical ventilation
7. Rate of re-hospitalization

First, the primary endpoint will be tested for superiority of pimodivir in combination with SOC over placebo in combination with SOC at the 2-sided 5% significance level.

The confirmatory test procedure follows the Serial Gate Keeping strategy as outlined in Section 7 of the FDA's draft guidance on Multiple Endpoints to control the overall type I error at the 5% 2-sided level. The primary and six most important secondary endpoints (listed above) will be tested in the hierarchical order per the 5 steps outlined below. All alphas and p-values specified are 2-sided.

Step 1: Test the primary hypothesis ("Hospital recovery scale at Day 6")

- If the p-value is $\leq 5\%$, continue to Step 2.
- If the p-value is $> 5\%$, stop testing, and no claim will be made.

Step 2: Test first set of 2 secondary endpoints (“Incidence in post-baseline complications” and “Time from start of study drug to hospital discharge”). The Bonferroni-Holm procedure will be applied to control the type I error within Step 2.

- If the smallest of the 2 p-values is $\leq 2.5\%$ and the largest of the 2 p-values is $\leq 5\%$, continue to Step 3.

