5.2.3. Analysis Methods

A proportional odds model will be used as primary model to analyze the hospital recovery scale on Day 6, modeling the common odds ratio of improvement on the ordinal scale of active treatment versus placebo. The model will include treatment, hospital recovery scale category at baseline and the stratification factors (NEWS2 category at screening, type of baseline SOC, and time since onset of influenza symptoms). In a first step equal slopes (i.e. proportional odds) for the treatment effect only and unequal slopes for the other covariates, will be modeled. If this model does not fit a full

proportional odds model will be applied, i.e. implying proportional odds for all covariates in the model. The common odds ratio from the final model will be considered as the estimate of the treatment effect. The actual values of the stratification factors will be used for all models, not as randomized. The proportional odds model will be defined in such a way that a common odds ratio smaller than 1 indicates larger improvement in the pimodivir treatment group.

Graphical displays and tabulations will be provided showing the proportion of subjects per hospital recovery scale category and day. Also, shift tabulations will be provided of the baseline hospital recovery scale category versus the post-baseline hospital recovery scale category, per day.

The proportional odds assumption will be assessed by testing for parallel slopes for the treatment effect only.

In addition, each of 5 dichotomizations of the hospital recovery scale, ie,

- Not hospitalized, vs worse (ie, hospitalized)
- Non-ICU hospitalized without supplemental oxygen (or better), vs worse
- Non-ICU hospitalized with supplemental oxygen (or better), vs worse
- In the ICU without invasive mechanical ventilation (or better), vs worse
- Invasive mechanical ventilation (or better), vs worse (ie, died)

will be analyzed using a logistic regression model, including treatment, hospital recovery scale category at baseline and stratification factors.

The hospital recovery scale will also be analyzed using the Van Elteren test with strata defined by the stratification factors^[3, 6].

A table will be created showing the number (%) missing HRS values at day 6 overall and by reason: study discontinuation: due to COVID-19 and not due to COVID-19, discharged against medical advice prior to day 5 and subjects that have no confirmed influenza A.

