ATTACHMENT 6. : HRS DERIVATION

The HRS categories should be evaluated from 6 to 1. First check if the subject falls in category 6 (has the subject died?) if not then we evaluate category 5, if not 5 then evaluate category 4 and so on.

The HRS is evaluated at baseline and per day, relative to the first study drug intake.

The baseline HRS is covering the full baseline/screening/day 1 visit which can occur on 2 days.

Timing of first study drug intake is not taken into account.

Note:

- VSOXYSAT is assessed 3 times per day (or per baseline visit). In case one of the assessments says 'N' then the final result for that day (or baseline visit) is 'N', else if one of the assessments is 'NA' then the final result is 'NA' else if one of the assessments is missing then final result is missing.

So a combination of 'Y', "", "N" → result ='N'

'Y', "", "NA" → result ='NA'

'Y','Y','' → result =''

'Y','Y','Y' → result ='Y'

On the baseline visit, on days at or after HO end date or on the day of discontinuation it might be that less than 3 assessments are done. Therefore, take only the records into account from the dataset on those days as planned. The same rules above apply to derive the final result per day when more than 1 assessment is collected.

- In case the subject withdrew from the study, the HRS will be set to missing from the next day onwards.
- In case of chronic oxygen use and multiple CMARTN values on a day we consider the worst value: In case one of the values is 'N' then final result for that day (or baseline visit) is 'N', else if one of the assessments is missing then final result is missing.
- The list of types of supplemental oxygen and invasive mechanical ventilation can be extended depending on the medical review (see DPS part 2 or Excel sheet of the medical review)
- The list of hospitalization terms (i.e.: ICU or WARD) can be extended depending on the medical review (see DPS part 2 or Excel sheet of the medical review).
- If the Subjects has no HO data, the subject is considered to be in the hospital during the trial. All other aspect of the HRS will be evaluated according to the derivation below.
- In case the readiness for discharge (RDISHOSP) is assessed more than once per day (baseline visit) we consider the worst value: in case one of the values is 'N' then the final result of that day (or baseline visit) is 'N'

Some clarification is required for following categories:

6. Death

When DM.DTHDTC<=(date of assessment)

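### The baseline hospital recovery score ignores first-dose time, so post-dose Day 1 events can enter the baseline covariate of the primary model

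*SAP*

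**What the plan says.** **General rule.** SAP 2.5: "The baseline analysis visit is defined as the last assessment before the first intake of the study drug", with listed exceptions.

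**HRS exception.** In the same section, "The baseline HRS is defined irrespective of the time of the start of study drug". The score covers the screening/baseline/Day 1 visit, which may run over two days, and is assigned to Day 1. SAP Attachment 6 repeats the point: "Timing of first study drug intake is not taken into account".

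**Scoring.** Under SAP 5.2.1 and Attachment 6 the score is the worst situation in the period, with categories checked from 6 down to 1. Death and invasive ventilation are matched by date, and ICU or ward stay by study day. None of these has a dose-time cut.

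**Dosing.** Protocol Section 6 gives one or two doses on Day 1.

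**Use.** SAP 5.2.3, on the primary model: "The model will include treatment, hospital recovery scale category at baseline and the stratification factors". The five dichotomised logistic models carry the same covariate, and the shift tables set post-baseline category against it. SAP 5.3.2.1 analyses Days 2 to 14 in the same way. For the primary model, protocol Section 11.4 requires at a minimum only treatment and the stratification factors.

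**The concern.** A baseline covariate should be fixed before treatment can act. Take a subject on the ward with oxygen (category 3) who is dosed in the morning and intubated that evening. Attachment 6 gives this subject a baseline of 5. If the drug influences such events within hours, in either direction, the model compares subjects within levels of a variable that already contains part of the effect. The Day 6 odds ratio then loses part of that early effect, and the shift table shows no change between a baseline of 5 and a later 5.

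A Day 1 death after dosing is the extreme case. By the date rule it scores 6 at baseline, and a baseline of 6 predicts Day 6 perfectly.

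The definition also sits badly with the rest of the SAP:

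- SAP 2.1.1 starts the treatment phase at first intake, so the evening intubation is a treatment-phase event.
- Under the general baseline rule the same event counts as mechanical ventilation started post-baseline (SAP 5.3.1.1).
- The post-dose exception for viral load in SAP 2.5 is capped at 30 minutes, applies only when no pre-dose value exists, and is flagged. The HRS exception has no cap, no such condition and no flag.

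**Working it through.** **1. Is the planned sample size affected?** Inputs are "assuming a benefit of approximately 38% reduction of the common odds ratio" (OR 0.62), a placebo Day 6 distribution of 30/30/25/5/5/5%, 90% power (all SAP 1.4), and testing "in combination with SOC at the 2-sided 5% significance level" (SAP 5.1.1). Under proportional odds the pimodivir distribution is 40.9/29.9/19.4/3.4/3.3/3.2%. The mean proportions p̄ give Σp̄³ ≈ 0.083. Whitehead's formula, which the SAP cites, is

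N = 12(z₀.₉₇₅ + z₀.₉₀)² / [ln(OR)² (1 − Σp̄³)] = 12 × (1.960 + 1.282)² / (0.478² × 0.917) ≈ 601.

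This reproduces the planned 600, with power of 89.9% at 600. Baseline HRS does not enter the formula, so the point leaves the planned size unchanged.

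**2. Yardstick.** The design implies SE(log OR) ≈ 0.478 / 3.24 = 0.147.

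**3. First illustration: discrete Day 1 deterioration.** The documents give neither a baseline HRS distribution nor a Day 1 effect, so these inputs are assumptions. Baseline is 80/12/8% in categories 3/4/5, post-dose Day 1 deterioration carries through to Day 6, and each scenario has 200,000 simulated subjects.

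| Day 1 deterioration, placebo vs active | Later OR | OR, pre-dose baseline | OR, SAP baseline | Shift in SE |
|---|---|---|---|---|
| 5% vs 2.5% | 0.62 | 0.60 | 0.62 | ln(0.62/0.60)/0.147 = 0.22 |
| 8% vs 4% | 0.62 | 0.59 | 0.62 | ln(0.62/0.59)/0.147 = 0.34 |
| 4% vs 8% (early harm only) | 1.00 | 1.07 | 1.00 | ln(1.07)/0.147 = 0.46 |
| equal in both arms | 0.62 | 0.64 | 0.63 | negligible |

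**4. Second illustration: early effect as a share of the Day 6 log odds ratio.** This is a latent-severity model with 120,000 subjects per setting and power rescaled to 600. The two values in each cell are for weaker and stronger dependence on underlying severity.

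| Share present on Day 1 | OR, pre-dose baseline | OR, worst score including post-dose | Power change (points) |
|---|---|---|---|
| 0% | 0.65 / 0.67 | 0.64 / 0.67 | +2 / +1 |
| 10% | 0.65 / 0.69 | 0.65 / 0.69 | −1 / −2 |
| 25% | 0.64 / 0.69 | 0.66 / 0.70 | −4 / −5 |
| 50% | 0.65 / 0.69 | 0.68 / 0.72 | −9 / −13 |
| 100% (extreme) | 0.64 / 0.68 | 0.70 / 0.76 | −18 / −26 |

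Here 0.62 is conditional on severity, so the fitted odds ratios lie nearer 1 and absolute power is below 90%. The two baselines differ in 10 to 23% of simulated subjects, which is a generous amount of contamination. The table shows direction and range only.

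**5. Type I error.** If the drug has no effect, Day 1 status is independent of the randomised arm whether or not it is measured after dosing. Adjusting for it then does not inflate the error rate.

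**The case against.** - **Procedures come before dosing.** Footnote b to protocol Time and Events Schedule 1, and protocol 9.1.2, put screening procedures before first intake. That governs conduct, but Attachment 6 does not use it as a boundary and says dose time is ignored. This does not rescue the definition.
- **A large effect within hours is unlikely.** Some subjects receive only an evening dose on Day 1. Protocol 1.1 places steady state between Days 3 and 4, and reports a Day 8 ordinal odds ratio of 1.03 (0.43 to 2.47) in the Phase 2 hospital study. The first illustration also puts at least 20% + 5% × 80% = 24% of placebo subjects in category 4 or worse on Day 1, against 15% assumed for Day 6. This stands, and is why the effect is judged probably small.
- **Early harm is hidden.** A reader might infer this, but the documents do not support it. A Day 1 death, or an intubation that persists, still counts in the Day 6 outcome; only its adjustment changes. Complications, mortality and adverse events are counted from first dose (SAP 5.3.1.1 and 7.1.1). Nor would an odds ratio of 1.07 be visible at 600 subjects under either baseline: its approximate 95% interval is exp(0.068 ± 1.96 × 0.147), or 0.80 to 1.43.
- **Some inputs have no time.** ICU need and discharge readiness are once-daily items (protocol 9.1.3), and SAP 5.3.1.1 says no time is available for readiness. Schedule 1 appears to have no screening entry for either, as far as the table can be read. This stands, so a dose-time cut alone is not enough.

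**Conclusion.** The definition lets post-dose Day 1 status into the baseline covariate of the confirmatory model, and this is avoidable. Its consequence is partial attenuation of any early effect, whether benefit or harm. The size cannot be derived from the documents. Under the assumed inputs the shift is about 0.2 to 0.5 standard errors. It is close to nil if the drug does little in the first hours, and grows only if a substantial share of the Day 6 effect is already present on Day 1.

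Two stronger readings should be set aside. The false-positive rate is not inflated when the drug has no effect. Nor does the problem reach every primary analysis: the Van Elteren test uses only the stratification factors (SAP 5.2.3), and it supplies the formal p-value if proportional odds fails for treatment (SAP 5.1.1). The change is worth making because the covariate belongs to the primary model and the correction is cheap, not because the result is shown to be seriously biased.

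**What to change.** 1. Derive the baseline HRS covariate from status up to first study drug intake, using the datetimes of ICU or ward stay and of oxygen and ventilation records, together with pre-dose oximetry. Make category 6 impossible at baseline.
2. For once-daily items without a time (ICU need, discharge readiness), use the screening/baseline entry if one exists. Otherwise, do not let a date-only Day 1 entry raise the category above what the timed pre-dose records support.
3. Report the full-day worst score separately as Day 1.
4. Add a sensitivity analysis of the primary model without baseline HRS, which is the minimum model in protocol Section 11.4.

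**Cost.** A short change to SAP 2.5 and Attachment 6, and a little derivation work. The SAP already computes ICU and ventilation times from the later of their start and first intake (5.3.1.1), and uses timed oxygen records for NEWS2 stratification (5.1.4). The downside is some possible misclassification of ICU need where only a date is recorded.
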